Introduction: Glycemic control in acutely ill stroke patients with hyperglycemia is vital. Although insulin is the choice of anti-diabetic agent during acute stage, it is not clear which insulin regimen is better in terms of glycemic control and prevention of hypoglycemia in hospitalized acute stroke patients who are usually on small frequent nasogastric tube feeding. The present study aims to evaluate the efficacy and safety of human insulin (regular insulin and neutral protamine hagedorn, NPH insulin) to analog insulin (basal insulin glargine and rapid acting insulin aspart) in hospitalized acute stroke patients with hyperglycemia.

Justification: Analog insulins are developed by minor alteration of the amino acid chain which alters their pharmacokinetics and make them more physiological. However, these insulins are costly and are not widely available. Conventional human insulins are more commonly used in our country. Comparison of these two regimen is necessary in our own setting to optimize optimal glycemic management of hospitalized acute stroke patients.

Methodology: In this single-center, open-label, randomized trial, 100 patients with acute stroke and hyperglycemia (capillary blood glucose ≥ 10 mmol/L on 2 or more occasions) or history of type 2 DM admitted in the in-patient Department of Neurology, National Institute of Neurosciences (NINS) & Hospital will be randomly assigned to receive human insulin or modern insulin therapy in 1:1 ratio. The study will be carried out from February to June 2021. Blood glucose (BG) will be monitored by standardized glucometer thrice a day and insulin dose will be adjusted daily. The primary outcome of the study will be the differences in glycemic control between groups, as measured by mean daily BG concentration during the hospital stay. Secondary outcomes include differences between treatment groups in any of the following measures: number of hypoglycemic events (BG < 3.9 mmol/L), total daily dose of insulin, length of hospital stay, hospital complications and mortality.

Expected outcome/ result: The result will clearly show the efficacy and safety of newer insulins in comparison to conventional human insulin.

Recommendation: The study may help generating recommendations about insulin use in hospitalized acute stroke patients.

Section-C

INTRODUCTION:

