In different countries, basal-bolus therapies with insulin analogs are being used more commonly. But intermediate-acting and regular human insulin are also observed to have almost similar efficacy and safety (12,14). No inpatient trials have been conducted in our region to determine optimal treatment regimens for hospitalized patients with T2DM in special situation like acute stroke. As there are significant differences in patient demographics, admission cause, feeding practice and availability of hospital resources between patients of developed and developing countries, the choice of agents may not be similar (15,16). In this background, the present study aims to compare the efficacy and safety of conventional human insulin (regular insulin and intermediate acting NPH insulin) to newer analog insulin (basal insulin glargine with rapid acting insulin aspart) in acute stroke patients with hyperglycemia admitted in a referral tertiary neuroscience institute of Dhaka.

RATIONALE:

One in five patients hospitalized for acute stroke has hyperglycemia. For optimum outcome of these patients, proper glycemic control is essential. Acute stroke patients, who need hospitalization, are usually unable to take food normally and they are fed through nasogastric tube with small frequent feeding (200 ml, 2-hourly, 10 feed/day). It is not clear which insulin regimen will suit better to these type of feeding practice. Moreover, corticosteroids (dexamethasone) are often used in these patients as treatment adjunct which further challenges glucose homeostasis. Different insulin regimens are used in such patients but none is validated in clinical trials. Episodes of hypoglycemia may cause further neurological deterioration in acute stroke patients. So regimen with less chance of hypoglycemia needs to be identified. Although analog insulins are observed to have less chance of hypoglycemia, they are costly and had not been well studied in our setting. It is essential for us to know the efficacy and safety of analog insulin regimen in comparison to human insulin, so that appropriate management decision can be made

OBJECTIVES:

General objective:

- To compare the efficacy and safety of human insulin (regular insulin and intermediate acting NPH insulin) to analog insulin (basal insulin glargine and rapid acting insulin aspart) in hospitalized acute stroke patients with hyperglycemia

Specific objectives:

In hospitalized acute stroke patients with hyperglycemia -

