- To evaluate the efficacy and safety of human insulin (regular insulin and intermediate acting NPH insulin)
- To assess the efficacy and safety of insulin analog (basal insulin glargine and rapid acting insulin aspart)
- To compare the efficacy and safety of two insulin regimen
- To evaluate the socio-demographic and clinical characteristics of the patients included in two treatment arms

METHODOLOGY:

Type of study: Single-center, open-label, randomized trial

Place of Study: Department of Neurology, National Institute of Neurosciences & Hospital, Dhaka.

Study Period: February to June, 2021

Study population: Patients admitted in the Department of Neurology with acute stroke and hyperglycemia

Sample Size:

Sample size was calculated according to following formula for non-inferiority trial (17):

$$N = 2 \times \left(\frac{Z_{1-\alpha} + Z_{1-\beta}}{\delta_0} \right)^2 \times S^2$$

Here, N= sample size per group

$$\alpha = 0.05$$

$$\beta = 0.20$$

δ_0 = a clinically acceptable margin (assumed as 3 mmol/L of blood glucose)

S² = Pooled standard deviation of both comparison group = 8

So,

$$N_{\text{non-inferiority}} = 2 \times \left(\frac{1.645 + 0.845}{3} \right)^2 \times 6^2 = 50$$

As a result, 50 patients will be randomly assigned to two treatment groups (50 human insulin regimen, 50 analog insulin regimen).

Inclusion criteria

- Patients admitted to adult neurology ward with acute stroke with
- Patients having hyperglycemia (capillary blood glucose ≥ 10 mmol/L in 2 or more occasions or having history of treatment for DM)
- Patients with age of 18-80 years of both sexes
- Patients or their attendants giving consent to take part in the study

Exclusion Criteria

- Patients with hyperglycemic emergencies (hyperglycemic hyperosmolar state or diabetic ketoacidosis)
- Pregnant patients
- Those not giving consent to participate in the study

Study Procedure

Patients will be randomly assigned to receive either a human insulin regimen (starting with regular insulin three times a day with NPH insulin twice a day) or analog insulin regimen (basal insulin glargine once daily and insulin aspart three times a day) following a computer-generated randomization table. All oral antidiabetic drugs will be discontinued on admission.

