Except anti-diabetic treatment, other treatments will be continued as per the decisions of the treating physicians. If NG feeding is discontinued and patient is kept NPO, conventional group will receive neutralizing insulin with any dextrose containing fluid along with low dose NPH insulin, if needed. Modern insulin group will receive neutralizing insulin with any dextrose containing fluid with glargine insulin as before.

After recruitment, each recruited patient will be visited daily (even in holidays according to a predefined schedule) by one of the investigators and insulin dose will be adjusted according to glucose profile of previous day. Insulin injection and capillary blood glucose monitoring by glucometer will be done by trained nurses as part of their routine patient care. Doctors and nurses on duty will be provided with cell number of the investigators who will receive call on 24/7 basis for any emergency or uncertainty regarding management of hyperglycemia.

Hypoglycemia is regarded as the only short-term adverse event of insulin. As both treatment arms will use established and recognized insulin regimen, no compensation will be provided to the patient or his/her attendants in case of any adverse event. As most of the hospitalized patients have severe stroke with case fatality rate around 20%, death will not be regarded as parameter of primary treatment outcome.

During discharge, last in-hospital insulin dose will be continued with education to the caregiver regarding insulin injection and glucose monitoring technique. No follow up visit is included in the study.

Protocol deviation and protocol violation:

Deviation to protocol will be recorded and reported to ethical committee as soon as possible. Failure to obtain informed written consent, use of incorrect insulin regimen, not fulfilling inclusion and exclusion criteria will be regarded as protocol violation and will be reported to ethical committee immediately. In case of protocol violation, the data of related participant will be discarded.

Outcome variables

The primary efficacy outcome of the study will be the differences in glycemetic control between groups, as measured by mean daily BG concentration during the hospital stay.

The primary safety outcome will be the frequency of hypoglycemic events (BG <3.9 mmol/L).

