Secondary outcomes include differences between treatment groups in any of the following measures: total daily dose of insulin, length of hospital stay, hospital complications, and mortality.

Data collection technique

Data will be collected in a predesigned questionnaire by the research team. The researchers will recheck randomly and blindly to verify the collected data.

Data management

All data will be compiled and edited meticulously by thorough checking and rechecking. All omissions and inconsistencies will be corrected and will be removed methodically.

Statistical analysis

Computer based statistical analysis will be carried out with appropriate techniques and systems by SPSS 22.0. Quantitative data will be expressed as mean and standard deviation or median and inter-quartile range; and qualitative data will be expressed as frequency and percentage. Continuous variables, analysis will be made by the Students T-test or Mann-Whitney *U* test. Categorical variables will be analyzed by the χ^2 test. All probabilities will be 2-tailed. Statistical significance will be accepted at $p \leq 0.05$.

Utilization of results

The result of study will be helpful for the physicians to choose appropriate insulin regimen in patients hospitalized with acute stroke having hyperglycemia. It will also help the policy makers in ensuring adequate supply of appropriate insulin that may help improve the outcome of patients.

FLOW CHART

Sl. No.	Job Title	Feb'21	Mar'21	Apr'21	May'21	Jun'21
1.	Questionnaire Validation	√				
2.	Data Collection	√	√	√		
3.	Data Analysis				√	
4.	Report writing and Printing				√	√
5.	Submission					√

ETHICAL IMPLICATIONS:

Prior to the commencement of this study, approval of the institutional review board (IRB) of National Institute of Neurosciences & Hospital, Dhaka will be sought. The aims and objectives of the study along with its procedure, risks and benefits of this study will be explained to the patients or attendants of the patients in easily understandable local language and then written consent will be taken from each. It will be assured that all information and records would be kept confidential.

Role of funding agency

The funding agency will have no role in protocol development, data collection, analysis, interpretation or writing the report. The authors will have full access to all study data and will have the final responsibility for the decision to submit for publication.

REFERENCES:

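### Hypoglycemia, the primary safety outcome, is to be judged by a bare two-tailed p-value; without a between-arm estimate and confidence interval it cannot support the promised safety conclusion

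*Combined protocol and SAP*

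**What the plan says.** In Section-C, Outcome variables: "The primary safety outcome will be the frequency of hypoglycemic events (BG <3.9 mmol/L"). The opening summary and the abstract for the ethics committee instead put it among the secondary outcomes, as a count: "number of hypoglycemic events (BG < 3.9 mmol/L), total daily dose of insulin, length of hospital stay, hospital complications and mortality".

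The Statistical analysis section has no sentence specific to hypoglycemia. It gives generic rules. Continuous measures get a t-test or a Mann-Whitney test. For the rest, the rule is: "Categorical variables will be analyzed by the χ^2 test. All probabilities will be 2-tailed". The threshold is p ≤ 0.05. Data are to be summarised as means, medians, or frequencies and percentages. No confidence interval is planned for any outcome.

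The Sample Size section uses a non-inferiority formula whose margin is "a clinically acceptable margin (assumed as 3 mmol/L of blood glucose"). The only error rates stated (α = 0.05, β = 0.20) belong to that calculation.

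On purpose, the Rationale says: "So regimen with less chance of hypoglycemia needs to be identified". The summary's Expected outcome says: "The result will clearly show the efficacy and safety of newer insulins in comparison to conventional human insulin".

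**The concern.** Comparing safety is half of the general objective. The Rationale warns that hypoglycemia may worsen neurological status, and Utilization of results directs the findings to physicians and to policy on insulin supply. Yet the only planned output for this comparison is whether p falls at or below 0.05.

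A small p-value would show that the arms differ, but not by how much. A large one would not separate two similar regimens from a trial too small to tell them apart. In neither case would the reader learn how large an excess of hypoglycemia, in either direction, remains compatible with the data. Correcting the blood-glucose analysis would leave this unchanged, because none of its margin, standard deviation or power applies to hypoglycemia.

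**Working it through.** **1. What the sample size covers.** The plan's figure is 2 × ((1.645 + 0.845)/3)² × 6² = 2 × 0.6889 × 36 = 49.6, so 50 per group. It reproduces with the 6 in the formula line. The 8 stated just above it does not match and needs reconciling as a separate matter. Every input concerns mean blood glucose; none concerns hypoglycemia.

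**2. What the test would miss.** The documents give no hypoglycemia rate, so the rates below are assumptions. Inputs: 50 per arm; outcome taken as patients with at least one event; Pearson χ², two-sided, p ≤ 0.05. For each pair of event counts (i, j), the binomial probabilities are multiplied and summed over all tables with p > 0.05. The true difference is a doubling throughout.

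| Assumed risks | Missed, uncorrected | Missed, continuity-corrected |
|---|---|---|
| 10% v 20% | 70% | 81% |
| 15% v 30% | 56% | 65% |
| 20% v 40% | 40% | 48% |
| 25% v 50% | 25% | 33% |
| 30% v 60% | 12% | 17% |

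The miss rate exceeds one half only when the lower-arm risk is below about 17% (between 19% and 20% with continuity correction). The data of protocol violators are to be discarded and the sample size has no inflation, so fewer may be analysed. With 40 per arm the uncorrected figures become about 75% at 10% v 20% and 50% at 20% v 40%.

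**3. If events are counted instead.** A rough guide is the log rate ratio, with variance (1/m + k)/50 + (1/(2m) + k)/50, where m is the assumed mean number of events per patient in the lower arm and k the assumed overdispersion. Power for a doubling is Φ(ln 2/√variance − 1.96). With m = 0.3 and k = 1 the variance is 0.0867 + 0.0533 = 0.140, and power is Φ(0.693/0.374 − 1.96) = 46%. For k from 0 to 2, power is 20–24% at m = 0.1, 37–59% at m = 0.3 and 46–81% at m = 0.5. The answer again depends on a rate the documents do not give.

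**4. What a p-value hides.** Take 10/50 v 18/50 as an illustration.
- χ² = 0.16²/(0.28 × 0.72 × 2/50) = 0.0256/0.008064 = 3.17, p = 0.075.
- Wilson 95% limits: 0.112 to 0.330 for 10/50; 0.241 to 0.499 for 18/50.
- Newcombe lower limit: 0.16 − √[(0.360 − 0.241)² + (0.330 − 0.200)²] = −0.016.
- Newcombe upper limit: 0.16 + √[(0.499 − 0.360)² + (0.200 − 0.112)²] = 0.324.

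The result is not significant, yet it is compatible with anything from a 2-point advantage to a 32-point excess.

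**5. Precision the trial can offer.** With equal observed proportions, the Newcombe 95% half-width is 12.7 points at 5/50, 15.7 at 10/50 and 17.5 at 15/50: about ±13 to ±18 points at assumed event rates of 10–30%.

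**The case against.** Sizing a trial on its efficacy outcome alone is ordinary practice, and a difference test suits the stated aim of identifying the regimen with less hypoglycemia. That stands. The plan also provides for frequencies and percentages, so if patients with an event are tabulated a reader could work out an interval. But the plan does not fix that unit: one section speaks of frequency of events and the abstracts of number of events. A primary safety result should not be left for readers to derive.

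Two stronger readings are tempting. The first is that a doubling of hypoglycemia would usually be missed. The documents give no baseline rate, and the statement holds only below about 17% in the lower-risk arm; at 25% v 50% and 30% v 60% the test would usually detect it. The second is that the plan equates p > 0.05 with comparable safety. It gives no interpretation of a non-significant result at all. That misreading is a foreseeable risk which nothing in the plan prevents, but it is not a stated rule.

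**Conclusion.** The point holds as one about what will be reported and concluded. For its primary safety outcome the plan offers a generic two-tailed p-value, leaves the unit of analysis open and gives the outcome conflicting status. That output cannot show which differences in hypoglycemia are excluded, so the promise of a clear safety result is not supported. This does not depend on any assumed rate.

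The size of the power shortfall does depend on one: at 50 per arm a true doubling is missed from 70% of the time (10% v 20%) down to 12% (30% v 60%), for the uncorrected χ² test on patients with at least one event. A reader might infer that the trial must therefore have a safety margin or be powered for hypoglycemia. The documents do not support that demand: the non-inferiority design concerns blood glucose, and no claim of equivalent safety is planned. This is a cheap improvement, not a reason to resize the trial.

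**What to change.** In Statistical analysis, add a paragraph such as:

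*The safety variable is the proportion of patients with at least one BG value below 3.9 mmol/L. The governing safety result is the between-arm risk difference with its two-sided 95% CI (Newcombe). The event rate ratio per patient-day, with a 95% CI from a model allowing for overdispersion, is supportive. Both confidence limits will be interpreted, since either regimen could be the worse. A p-value above 0.05 will not be read as equal or comparable safety.*

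Give hypoglycemia the same status in Outcome variables and in both abstracts. In Expected outcome, replace the promise of a clear demonstration of safety with a statement that the trial will estimate the difference in hypoglycemia, with a precision of about ±13 to ±18 percentage points at assumed event rates of 10–30%, and that the sample size was not set for this outcome.

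The cost is some wording and a few intervals from data already collected, with no extra patients or procedures. The safety claim becomes more modest: the report may have to say that a relevant excess of hypoglycemia cannot be excluded.

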Abstract for IRB/Ethical Committee:

Glycemic control in acutely ill stroke patients with hyperglycemia is vital. Although insulin is the choice of anti-diabetic agent during acute stage, it is not clear which insulin regimen is better in terms of glycemic control and prevention of hypoglycemia in hospitalized acute stroke patients who are usually on small frequent nasogastric tube feeding. The present study aims to evaluate the efficacy and safety of human insulin (regular insulin and neutral protamine hagedorn, NPH insulin) to analog insulin (basal insulin glargine and rapid acting insulin aspart) in hospitalized acute stroke patients with hyperglycemia. In this single-center, open-label, randomized trial, 100 patients with acute stroke and hyperglycemia (capillary blood glucose ≥ 10 mmol/L on 2 or more occasions) or history of type 2 DM admitted in the in-patient Department of Neurology, National Institute of Neurosciences (NINS) & Hospital will be randomly assigned to receive human insulin or modern insulin therapy in 1:1 ratio. The study will be carried out from February to June 2021. Blood glucose (BG) will be monitored by standardized glucometer thrice a day and insulin dose will be adjusted daily. The primary outcome of the study will be the differences in glycemic control between groups, as measured by mean daily BG concentration during the hospital stay. Secondary outcomes include differences between treatment groups in any of the following measures: number of hypoglycemic events (BG < 3.9 mmol/L), total daily dose of insulin, length of hospital stay, hospital complications and mortality. Computer based statistical analysis will be carried out by SPSS 22.0. Quantitative data will be expressed as mean and standard deviation or median and inter-quartile range; and qualitative data will be expressed as frequency and percentage. Continuous variables will be compared by the Students T-test or Mann-Whitney *U* test. Categorical variables will be analyzed by the χ^2 test. All probabilities will be 2-tailed. Statistical significance will be accepted at $P \leq 0.05$. Prior to the commencement of this study, approval of the institutional review board (IRB) of NINS will be sought. The aims and objectives of the study along with its procedure, risks and benefits of this study will be explained to the patients or attendants of the patients in easily understandable local language and then written consent will be taken from each. The result of the study may help us to choose appropriate insulin regimen for hospitalized acute stroke patients in our setting.
